Dose Higher-doses of botulinum toxin show better intensity and duration in the treatment of Gummy Smile?

This study is registered at clinicaltrials.gov (NCT05127018).

Document Date: November 20, 2019

Study Protocol :

The smile is one of the universal facial expressions of humans. Gingival smile is characterized by gingival exposure of >3 mm upon smiling. The degree of gingival exposure can vary substantially between patients, with patients presenting gingival exposure of up to more than 10 mm. The prevalence of gingival smile is 10.57%, and it is more frequently observed in females. Although gingival smile is merely an anatomical variation, it can be considered unattractive, causing significant distress and impacting one's quality of life. Moreover, most orthodontists and dentists regard gingival smile as an important risk factor for dental treatment.

Gingival smile involves a complex interaction between the facial muscles, bone, and skin; specifically, it is related to hypermobility of the upper lip with muscle involvement and alterations in anatomical features, such as a short clinical dental crown, anterior dentoalveolar extrusion, maxillary excess, and a short upper lip. Therapies for gingival smile range from botulinum toxin injections to surgical interventions according to its etiology. Although the outcomes of surgical procedures are long-lasting, botulinum toxin type A treatment is an easy and fast outpatient procedure that requires no downtime and has high efficacy rates. Nevertheless, there are controversies around the optimal dose and injection site of botulinum toxin type A. Moreover, the efficiency of botulinum toxin type A for gingival smile varies markedly between studies, with the improvement rate of gingival exposure ranging from 62.06% to 98%. Sucupira and Abramovitz advocate the use of a low amount of botulinum toxin type A of 1.95 U per side for the treatment of gingival smile. They noted an average satisfaction level of 9.75 on a 10-point scale with this approach. They claimed that higher doses did not provide further benefit, and, in fact, could lead to lip ptosis, asymmetry, and

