excessive upper lip length. However, Polo disagreed with their argument, claiming 2-5 U injection of botulinum toxin type A according to the severity of gingival smile. In this regard, Garcia and Fulton showed that low-dose injection of botulinum toxin per muscle (2-5 IU) was as effective as higher doses. Though prior studies have demonstrated a correlation between higher doses of botulinum toxin and intensity and duration of muscle paralyses, no conclusion can be drawn regarding duration and intensity of doses used in the recent studies. A safe approach advocated by some authors consists of starting with low toxin doses initially, with retouching at a later stage if required. In this study, the investigators compared botulinum toxin type A efficiency using the average-dose method (2-5 U botulinum toxin type A per side determined according to the severity of anterior gingival smile) and, the higher-dose method (3-10 U botulinum toxin type A per side determined according to the severity of anterior gingival smile). The investigators aimed to assess the efficiency and duration of these approaches, as well as side effects and patients' satisfaction with treatment. In this prospective self-controlled study, healthy participants with gummy smile underwent two treatment methods.

The inclusion criteria to be considered for the study were as follows: 1) healthy participants with anterior gingival exposure of ≥ 3.0 mm during unrestricted, "full-blown" smiling; 2) participants between 18 and 60 years old. The following exclusion criteria were used for the study participants: 1) complications to botulinum toxin A; 2) paralysis of the face; 3) previous disease and/or treatment that affected the position of the gingiva or upper lip; 4) botulinum toxin A injection in the head or neck region within the previous year; 5) are currently receiving or have received active orthodontic treatment, including vertical dimension treatment, for extrusion or intrusion; 6) occurrence of periodontal disease; 7) refused to participate; 8) loss to follow-up.

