First, participants were injected with the average-dose, which the dose was individualized according to the severity of anterior gingival exposure pretreatment. For mild gingival smile (3-5 mm), a single-site injection of 2 U botulinum toxin type A [total, 4 U] at both the right and left levator labii superioris alaeque nasi muscles) was administered. For moderate (5-7 mm) and severe (≥ 7 mm) gingival smile, 3 U and 5 U of botulinum toxin type A, respectively,

were injected per side (total, 6 U and 10U, respectively). The injection points were located at bilateral levator labii superioris alaeque nasi muscles and at the Yonsei point, with half doses administered at each point. Data were collected at baseline and at four, 12, 48, weeks follow-up.

And 8 months after the first injection, all the patients underwent second injection of the higher-dose method.

With this method, patients were administered botulinum toxin type A after 8 months when the effect of the previous injection had vanished. The injection dose (U) per side was set as the absolute value of the preoperative anterior gingival exposure (mm). For example, if the preoperative anterior gingival exposure was 5mm, then the patient would be injected with 5 U of botulinum toxin per side (total, 10U). The injection points were located at bilateral levator labii superioris alaeque nasi muscles and at the Yonsei point, with half doses administered at each point. Data were collected at baseline and at four, 12, 48, weeks follow-up.

Statistical Analysis Plan :

Data entry will be managed using WJX procedure (Ranxing Information Technology Co., Ltd., Changsha, China) and accuracy was ensured by double entry and validation. All statistical analyses were performed using SPSS software v. 20.0 (IBM Corp., Armonk, NY). The mean and standard deviation were used to describe normally distributed numerical values, and a paired-samples t-test was used to identify differences. The Wilcoxon signed-rank test was used for non-normally distributed numerical values, and the McNemar-Bowker test was used to compare dichotomous variables. A P value of <0.05 was considered statistically significant.

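### Duration is a stated aim, but with visits only at weeks 4, 12 and 48 and re-injection at 8 months, two doses that both wear off after week 12 cannot be told apart

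*Combined protocol and SAP*

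**What the plan says.** The title asks whether "Higher-doses of botulinum toxin show better intensity and duration in the treatment of Gummy Smile", and the Study Protocol repeats the aim: "The investigators aimed to assess the efficiency and duration of these approaches".

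The same visit sentence closes the description of each dose method: "Data were collected at baseline and at four, 12, 48, weeks follow-up". On timing, "8 months after the first injection, all the patients underwent second injection of the higher-dose method", and the higher dose is given "after 8 months when the effect of the previous injection had vanished". The protocol does not say when the second baseline is measured relative to the second injection, or when the higher-dose effect is expected to end.

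The Statistical Analysis Plan names a paired t-test and the Wilcoxon signed-rank test for numerical values, and adds that "the McNemar-Bowker test was used to compare dichotomous variables". It gives no duration endpoint, no definition of return to baseline and no method for time to return. It also gives no sample size, SD or expected duration.

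**The concern.** To compare durations, the visits must show for enough patients which effect ended first. After the higher dose no visit falls between weeks 12 and 48. After the average dose the only look past week 12 that is free of the second injection is the second baseline, if it was taken just before that injection. If both effects end inside these gaps, both doses read as present at week 12 and absent at the next look, whatever the true difference.

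Two errors in opposite directions are possible. A real difference could be missed. A difference could also be manufactured, because the next look comes at about week 35 for one dose and week 48 for the other. Separately, treating period-1 week 48 as an average-dose result would credit higher-dose effect to the average dose.

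**Working it through.** The plan has no duration figure to reproduce, so the check is a timeline followed by an illustration under stated assumptions.

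**Timeline (document inputs only)**

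- Second injection: 8 × 365.25 / 12 / 7 = 34.8 weeks after the first (32 weeks if a month is taken as 4 weeks).
- Period-1 week 48: 48 − 34.8 = 13.2 weeks after the higher dose (48 − 32 = 16 on the other convention). The period-2 week-12 visit falls at 34.8 + 12 = 46.8 weeks from the first injection, so period-1 week 48 comes just over a week after it.
- Unobserved stretch after week 12: 48 − 12 = 36 weeks for the higher dose; 34.8 − 12 = 22.8 weeks for the average dose (20 on the 4-week convention).

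**What a patient's record can show**

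A patient with effect at week 12 and none at the next look has a loss interval of (12, 34.8] on the average dose and (12, 48] on the higher dose. The intervals overlap, so order is unknown. True durations of 16 and 32 weeks give the same record as 20 and 20.

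The unequal upper ends also make simple scoring unsafe. With identical true durations inside the gap, scoring the first visit without effect gives 48 − 34.8 = 13.2 weeks in favour of the higher dose. Interval midpoints give (12 + 48)/2 − (12 + 34.8)/2 = 30 − 23.4 = 6.6 weeks.

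**Size, under assumptions**

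Assumed: n=30, paired normal durations, SD 4 weeks, correlation 0.5. A patient is ordered only if the two loss intervals do not overlap. The test is an exact two-sided sign test on ordered patients at 0.05. Current looks are weeks 4, 12 and 34.8 in period 1, and 4, 12 and 48 in period 2. Revised looks add week 24 in period 1, and weeks 24 and 34.8 in period 2. Each power is from 20,000 simulated trials.

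| Mean duration, average v higher (weeks) | Current power | Revised power |
|---|---|---|
| 12 v 18 | 99% | >99% |
| 14 v 20 | 87% | 99% |
| 16 v 22 | 30% | 99% |
| 18 v 24 | 1% | >99% |
| 20 v 26 | 0% | >99% |
| 24 v 30 | 0% | >99% |
| 28 v 40 | 0% | 100% |

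The 20 v 26 row can be checked by hand. Under the current schedule a patient is ordered essentially only if the average-dose effect ends by week 12: P(Z < (12 − 20)/4) = P(Z < −2) = 2.3%, or 30 × 0.023 = 0.7 patients. The sign test needs at least 6 ordered patients, all in one direction (2 × 0.5⁶ = 0.031; 2 × 0.5⁵ = 0.063). About 98% of patients cannot be ordered now, against about 42% under the revised schedule.

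Other assumptions, current v revised:

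- SD 6, n=30: 79% v 97% at 14 v 20 weeks; 3% v 97% at 20 v 26.
- SD 6, n=20: 49% v 83% at 14 v 20; <1% v 83% at 20 v 26.
- SD 4, n=15: 25% v 66% at 14 v 20.
- Smaller differences (SD 4, n=30): 22% v 27% at 14 v 16; 0% v 26% at 20 v 22; 15% v 46% at 16 v 19; 0% v 62% at 20 v 23.
- Equal durations: the revised schedule rejects in about 2% of trials, so its gain does not come from a raised type I error.

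**The case against.** The strongest reply is that the schedule is coarse, not empty. It brackets each duration as up to 4, 4–12, or 12 to about 35 or 48 weeks, and it performs well when the average-dose effect ends near week 12 (99% at 12 v 18 weeks). Exposure in mm at week 12 can also be compared with the tests the plan names and may hint at persistence. This stands, and it limits the concern to doses that both wear off in the gap. Week-12 exposure is indirect, however: a deeper effect and a longer one look alike there, and the title asks about intensity and duration separately.

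Second, the power figures rest on assumed n, SD, correlation and durations, and on a test the plan does not name. The 6- and 12-week differences also flatter the revised schedule, which gains much less at 2–3 weeks. That is fair. The overlap of intervals and the week-48 conflict need none of these assumptions.

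Third, the 36-week gap takes week 48 at face value, although that visit is itself in conflict with the second injection. A transcription slip is possible, but no other visit time appears in the document, so the size is conditional on that reconciliation.

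Fourth, every patient receives the average dose first. Better visits would not separate dose from order; that limit remains after the fix.

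**Conclusion.** The concern holds. From the document alone, period-1 week 48 falls after the second injection, nothing is measured on the higher dose between weeks 12 and 48, and no duration endpoint or method is defined. Within the gap, duration can be bracketed but the doses cannot be compared.

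How much this costs depends on when the effects end, which the plan does not say. With n=30, SD 4 and a 6-week difference, little is lost if the average-dose effect ends around week 12, most of the power is gone when it ends at week 16, and virtually all from week 18 on. Comparisons of intensity, side effects and satisfaction at weeks 4 and 12 are not touched by this gap. The point should be corrected because duration is a headline question. Confidence in its practical size is medium.

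**What to change.** - In both periods, take the same smile measurement at week 24 and at 8 months. In period 1 the 8-month measurement is the second baseline; state that it is taken just before the second injection.
- Keep week 48 in period 2, where it is the only visit that could show a very long higher-dose effect. Do not use period-1 week 48 as an average-dose result, and reconcile that visit with the 8-month second injection.
- Define return to baseline in advance, against each injection's own baseline.
- Compare doses on interval-censored time to return, paired within patient; a sign test on patients whose intervals can be ordered is one option. Treat change at week 24 as supporting evidence only, since it mixes intensity with duration.
- Do not rely on week 24 alone: McNemar power on present/absent status there (SD 4, n=30) is >99% at 20 v 26 weeks but 30% at 14 v 20 and 34% at 28 v 40.
- If follow-up is already complete, as the past tense of the document may suggest, limit the duration claim to what was observed at weeks 4 and 12, the second baseline, and period-2 week 48.

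The cost is a schedule and SAP amendment with no new procedure: one extra measurement in period 1 and two in period 2. The downside is more visits per patient and more chance of missed ones, which matters because loss to follow-up is an exclusion criterion. The fallback wording costs nothing.

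### As scheduled, the average-dose week-48 visit falls about 13 to 16 weeks after everyone has had the higher dose, so week 12 is the last matched follow-up visit before re-injection

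*Combined protocol and SAP*

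**What the plan says.** Each participant receives both doses: "In this prospective self-controlled study, healthy participants with gummy smile underwent two treatment methods". The Study Protocol gives the average dose first and follows it with "Data were collected at baseline and at four, 12, 48, weeks follow-up". The same sentence appears again, word for word, after the description of the higher dose.

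The gap between injections is stated twice, in different words: "And 8 months after the first injection, all the patients underwent second injection of the higher-dose method", and "patients were administered botulinum toxin type A after 8 months when the effect of the previous injection had vanished".

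The aims include duration: "The investigators aimed to assess the efficiency and duration of these approaches". The title also asks whether higher doses "show better intensity and duration in the treatment of Gummy Smile".

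The Statistical Analysis Plan gives generic paired methods, such as "a paired-samples t-test was used to identify differences", with alternatives for non-normal and categorical data. It names no endpoint or visit, and has no rule for measurements taken after the second injection.

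**The concern.** Week 48 is later than 8 months. If both timings are meant literally, the last average-dose visit takes place when the participant is already under the higher dose. Week 48 is also the only follow-up visit after week 12, so it is the natural place to look for a difference in duration.

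In a self-controlled design with paired tests, pairing visits that carry the same label is an easy step, and nothing in the Statistical Analysis Plan prevents it. At week 48 that pairing would credit any remaining higher-dose effect to the average dose. This would tend to hide a longer duration of the higher dose, if there is one.

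**Working it through.** **Inputs.** From the Study Protocol: second injection 8 months after the first, in all participants; visits at baseline and weeks 4, 12 and 48 in each period; average dose always first; effect of the first injection said to be gone by 8 months. The plan gives no figure for the overlap and no visit windows, so there is nothing of its own to reproduce.

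**Week of the second injection**
- Calendar months: 8 × 365.25 / 12 / 7 = week 34.8
- 30-day months: 240 / 7 = week 34.3
- 28-day months: 8 × 4 = week 32

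**Average-dose week 48 relative to the second injection**
- Calendar months: 48 − 34.8 = 13.2 weeks after
- 30-day months: 48 − 34.3 = 13.7 weeks after
- 28-day months: 48 − 32 = 16 weeks after

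The higher-dose week-12 visit is at study week 32 + 12 = 44.0 to 34.8 + 12 = 46.8. Average-dose week 48 is thus only 48 − 46.8 = 1.2 to 48 − 44.0 = 4.0 weeks later than that visit.

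**What remains before re-injection**
- Week 12 precedes the second injection by 32 − 12 = 20 to 34.8 − 12 = 22.8 weeks. No follow-up visit is scheduled between week 12 and the higher-dose baseline.
- The higher-dose baseline, at about week 32 to 35, is still an uncontaminated reading after the average dose. No higher-dose visit is scheduled at that elapsed time.
- One of the three average-dose follow-up visits is therefore lost, and week 12 is the last matched one.

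**What would remove the overlap.** Week 48 stays clean only if re-injection comes at 48 weeks or later: 48 × 7 / (365.25 / 12) = 11.0 calendar months.

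**Direction, if week 48 is compared between doses.** Let A(t) and H(t) be the expected effects t weeks after the average and higher dose. Assume A has gone by 8 months, H wanes, and there is no cumulative or period effect.
- Clean contrast: H(48) − A(48) = H(48) − 0, which is zero or more.
- Contrast as scheduled: H(48) − H(13 to 16), which is zero or less.
- Difference: H(13 to 16). This is zero if no higher-dose effect remains at that time, and otherwise the whole effect then present. The documents give no effect size, SD or time course, so it cannot be narrowed.

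**The case against.** **A slip is possible.** The 8 months is stated in two differently worded sentences, while the 48 sits in one sentence used twice, so a single error could have been copied. The documents do not settle which figure is wrong. If one is, a short correction may be enough and the bias argument falls away. The text still needs that correction.

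**No contaminated analysis is specified.** This stands. A reader might infer that the planned analysis is biased, but the Statistical Analysis Plan names no visit, so the documents show a schedule conflict and a missing safeguard, not a biased contrast.

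**The loss is limited.** This stands in part. The higher-dose baseline gives a clean late reading after the average dose. If the effect has gone by then, a clean week-48 value would be near null anyway. Higher-dose week 48 is not overlapped by any later injection and remains usable for description. What is missing is a comparison at the same elapsed time after week 12.

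**Two other inferences go too far.** A reader might conclude that week 48 could never favour the higher dose. That direction concerns expected values under the assumptions listed in the working, and an observed contrast can go either way by chance. A reader might also conclude that weeks 4 and 12 isolate the effect of dose. The schedule shows only that they precede the second injection. The order is fixed, and mild cases get a single-site average dose while the higher-dose text describes two injection points.

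**The exclusion criterion adds nothing.** Exclusion criterion 4 ("botulinum toxin A injection in the head or neck region within the previous year") might be read as a washout that the schedule breaks. It is an entry rule with no stated reason, and does not govern visits within the study.

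**Conclusion.** The conflict is certain on the text as written, and should be fixed. Average-dose week 48 falls about 13 weeks after the higher dose (up to 16 with 28-day months) for every participant treated on schedule, and so cannot measure the average dose. The comparison at weeks 4 and 12 is not touched by this overlap. A matched comparison of duration beyond week 12 is not available.

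Bias is conditional on the week-48 value being used as average-dose data. In that case the week-48 contrast would be expected not to favour the higher dose, provided that the average-dose effect has gone by 8 months, the effect wanes, and there is no cumulative or period effect. Confidence is high for the timing conflict only, not for the presence or size of any bias.

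**What to change.** 1. Establish whether 48 or 8 months is a slip. If so, correct it so that the last average-dose visit precedes the second injection.
2. Add to the protocol and the Statistical Analysis Plan: *No measurement taken after the second injection is analysed as average-dose data. Week 48 is not compared between doses.*
3. If both timings are literal, replace average-dose week 48 with a late visit before re-injection, for example week 24. Add the same visit to the higher-dose period, make the late paired comparison there, and keep higher-dose week 48 for description only. The value just before the second injection may be paired with an added 8-month higher-dose visit only if re-injection took place at a fixed 8 months. If it waited until the effect had gone, that value is null by selection, the pairing would favour the higher dose, and it should not be used.
4. The protocol is written largely in the past tense. If visits are already complete, limit matched-time comparisons between doses to weeks 4 and 12. Report the second-period baseline and higher-dose week 48 descriptively, and draw no matched-time conclusion on duration beyond week 12.

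**Cost.** Steps 1, 2 and 4 change text only. Step 3 moves one visit and adds one. With week 24, the average-dose visit is 32 − 24 = 8 to 34.8 − 24 = 10.8 weeks before re-injection, and its higher-dose counterpart is at study week 32 + 24 = 56 to 34.8 + 24 = 58.8. Higher-dose week 48 stays at study week 32 + 48 = 80 to 34.8 + 48 = 82.8, so the study is not lengthened. The optional 8-month higher-dose visit would be one more, at study week 2 × 32 = 64 to 2 × 34.8 = 69.6. A single late visit compares the effect remaining at that time but does not locate when either effect ends. Week 24 is only an example, because the documents give no time course from which to choose the best week.

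### The average-dose week-48 visit falls about 13 weeks after the higher-dose injection, and the fixed order leaves dose inseparable from being second

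*Combined protocol and SAP*

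**What the plan says.** The Study Protocol section fixes one order for everyone. It begins "First, participants were injected with the average-dose", with units set by the severity of exposure, and continues "And 8 months after the first injection, all the patients underwent second injection of the higher-dose method".

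The visit sentence, "Data were collected at baseline and at four, 12, 48, weeks follow-up", appears twice, once under each method. On the gap between injections, the text says that "patients were administered botulinum toxin type A after 8 months when the effect of the previous injection had vanished". It gives no criterion for that return and no comparison that would check it.

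The injection technique also differs. Under the average dose, mild cases (3-5 mm) have one site per side. The higher-dose method divides the dose equally between two points per side and makes no exception for mild cases.

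On purpose, the protocol says "The investigators aimed to assess the efficiency and duration of these approaches", and the title asks about both intensity and duration. The Statistical Analysis Plan section says that for normally distributed values "a paired-samples t-test was used to identify differences". It adds the Wilcoxon signed-rank and McNemar-Bowker tests, but names no variables, time points or contrasts. No randomised order or concurrent control is described.

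**The concern.** Week 48 is the only scheduled average-dose follow-up visit after week 12, so it is where a reader would look for average-dose duration. By then the participant has already had the higher dose. A comparison of that visit with the pretreatment baseline, or with the higher dose's own week 48, would not measure what its label says. If the higher-dose effect fades between about 13 and 48 weeks, a between-method comparison at week 48 would favour the average dose for a reason unrelated to its duration.

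Weeks 4 and 12 are free of that overlap, but the order is the same in everyone. A paired difference there would naturally be credited to dose, although it also contains whatever comes with being the second injection and, in mild cases, with the added site.

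**Working it through.** The documents give no figure for the overlap, so there is nothing to reproduce. The inputs are the 8-month interval and the visits at weeks 4, 12 and 48, all from the Study Protocol section.

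**1. Week of the second injection.** With an average month of 365.25 / 12 = 30.4375 days, 8 × 30.4375 / 7 = 34.8 weeks.

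**2. Average-dose week 48, counted from the higher dose** (48 minus the week of the second injection):

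| Reading of 8 months | Second injection (week) | Week 48 falls after it by |
|---|---|---|
| Average month | 34.8 | 13.2 weeks |
| Calendar, 242 to 245 days | 34.6 to 35.0 | 13.4 to 13.0 weeks |
| 30-day months (240 days) | 34.3 | 13.7 weeks |
| 4-week months | 32.0 | 16.0 weeks |

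None of these readings removes the overlap.

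**3. Where the higher-dose visits fall.** Higher-dose week 12 is study week 34.8 + 12 = 46.8, which is 48 − 46.8 = 1.2 weeks before the average-dose week-48 visit. Higher-dose week 48 is study week 34.8 + 48 = 82.8. A week-48 comparison between methods would therefore set 13.2 weeks against 48 weeks after the same injection.

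**4. What remains for each method.** The average dose can be observed before re-injection at weeks 4 and 12 and at the baseline before the second injection (about week 35). The higher dose has weeks 4, 12 and 48. Only weeks 4 and 12 match.

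**5. Order.** Take columns for intercept, dose and period. With one sequence the two rows are (1, 0, 0) for the average dose given first and (1, 1, 1) for the higher dose given second. The dose and period columns are identical, so the rank is 2 for 3 parameters. The mean paired difference equals the dose effect plus the second-injection effect, plus any carryover. In mild cases it also includes the effect of going from one site to two. Any such effect enters the dose estimate one for one, and no added model term can separate it. With both sequences present the rank would be 3.

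**The case against.** The strongest reply is that the plan never commits to the harmful comparison. The Statistical Analysis Plan section names tests but no time points, and the paired tests might be baseline-to-follow-up within each method. The visit sentence is word for word the same under both methods, so 48 may be copied text or a wrong number. Both points stand. The between-method comparison at week 48 can only be put conditionally, and if the intended visit precedes re-injection the overlap disappears. The order problem would remain.

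The order may also be deliberate. The background notes: "A safe approach advocated by some authors consists of starting with low toxin doses initially, with retouching at a later stage if required". That is a fair reason for giving the lower dose first. It limits what may be concluded but does not show the comparison to be wrong.

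Three stronger readings are tempting, and the documents do not support them:

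- *The first injection's effect carried over.* The text asserts that it had gone and plans a second baseline. The lack of a criterion means the assertion is unchecked, not that it is false.
- *Any improvement at the average-dose week-48 visit is due wholly to the higher dose.* That follows only if the asserted washout is true. The visit is unusable for average-dose duration either way.
- *The fixed order favours the higher dose.* Nothing in the documents gives the size or direction of a second-injection effect.

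**Conclusion.** The point holds for the text as written, and it affects every participant. The average-dose week-48 value falls about 13 weeks after the higher dose and cannot inform average-dose duration. This rests on two assumptions: that 48 is the intended week, and that the visit was to be kept as an average-dose visit. The misleading between-method result at week 48 is conditional on that comparison being made, and its direction depends on the higher-dose effect fading between about 13 and 48 weeks.

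Separately, and whatever 48 was meant to be, the paired differences at weeks 4 and 12 estimate the higher-dose method given second against the average-dose method given first. They do not isolate dose. A complete washout would remove carryover but not an effect of being the second injection, nor the change of technique in mild cases. A reader might infer that the study can say nothing about the two methods. That goes too far: the comparisons at weeks 4 and 12 remain usable under a narrower conclusion.

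**What to change.** With data already planned:

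(a) Do not use the first-period week-48 value as an average-dose result. If 48 is a slip, correct it. Use the baseline before the second injection, at about week 35, as the last average-dose time point.

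(b) Report the paired difference in gingival exposure between the second and first baselines, with a 95% CI, as a check of the asserted washout.

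(c) Word the conclusion as concerning the higher-dose method, two-site in all participants, given as a repeat injection 8 months after the average-dose method and always second.

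The cost is one further paired estimate and a narrower claim, with no new visits. The downside is that these steps do not repair the duration question. The higher dose has no visit near week 35, so only weeks 4 and 12 remain matched, and duration beyond week 12 cannot be compared at a matched time.

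Restoring a matched late comparison, or separating dose from order, would need changes that are not cheap and that require a study still open. A visit about 35 weeks after the higher dose (study week 2 × 34.8 = 69.6) would give the matched time point. Randomising the order would separate dose from period, but would give up starting low for some participants.

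### All tests share one P<0.05 threshold with no primary comparison or multiplicity control; with 7 to 10 tests (assumed), a chance finding has roughly an 18–40% probability, or 9–22% in favour of the higher dose

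*Combined protocol and SAP*

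**What the plan says.** The aims are near the end of the Study Protocol's background text: "The investigators aimed to assess the efficiency and duration of these approaches, as well as side effects and patients' satisfaction with treatment". None is placed above the others. The follow-up schedule is given once for each injection, in the same words: "Data were collected at baseline and at four, 12, 48, weeks follow-up".

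The Statistical Analysis Plan then assigns tests by type of variable. For normally distributed values "a paired-samples t-test was used to identify differences"; the Wilcoxon signed-rank test replaces it for non-normal values; and "the McNemar-Bowker test was used to compare dichotomous variables". The section closes with its only decision threshold: "A P value of <0.05 was considered statistically significant".

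The plan does not say whether tests are one- or two-sided, how many there are, or which outcomes are tested at which visit. It gives no primary endpoint or visit, no order of testing, no repeated-measures model and no adjustment for multiple tests.

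**The concern.** The title asks whether higher doses work more strongly and for longer, and the background describes this as a point on which earlier authors disagree. To settle it, the reader needs to know in advance which comparison answers the question. Here a significant result on any outcome at any visit could be put forward as the answer, and a non-significant one passed over, without departing from the plan. The 5% error rate suggested by the threshold then applies to each test singly but not to the trial's conclusion.

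Errors in both directions matter. A false difference for the higher dose would support its use. A false difference against it, for example in side effects, would support the contrary view cited in the background, that higher doses add nothing and may do harm.

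**Working it through.** The plan states no familywise error rate, sample size or power, so there is no figure of its own to reproduce.

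**Inputs from the documents**
- Threshold per test: 0.05 (Statistical Analysis Plan).
- Aims: 4, unranked (Study Protocol).
- Follow-up visits per injection: 3, at weeks 4, 12 and 48 (Study Protocol).
- Second injection: 8 months after the first (Study Protocol).

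**Assumptions not in the documents**
- Tests are two-sided.
- No true difference exists on any outcome (global null).
- The test statistics are normal with a common correlation ρ between 0 and 0.7.
- The number of tests is k. Exposure, side effects and satisfaction at three visits plus one duration comparison give 3 × 3 + 1 = 10. Without week 48, 3 × 2 + 1 = 7. One test per aim gives 4.

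**Formulas**
- Independent tests, either direction: 1 − 0.95^k.
- Independent tests, favouring the higher dose only: 1 − 0.975^k, because half of each two-sided 0.05 lies on that side.
- Correlated tests, either direction: 1 − ∫ [Φ((1.96 − √ρ·x)/√(1−ρ)) − Φ((−1.96 − √ρ·x)/√(1−ρ))]^k φ(x) dx, by numerical integration. For the higher dose only, the second Φ term is dropped.

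**Results: chance of at least one false significant difference, either direction / favouring the higher dose**

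| k | ρ = 0 | ρ = 0.5 | ρ = 0.7 |
|---|---|---|---|
| 1 | 5% / 2.5% | 5% / 2.5% | 5% / 2.5% |
| 4 | 18.5% / 9.6% | 15.6% / 7.8% | 13.0% / 6.5% |
| 7 | 30.2% / 16.2% | 23.0% / 11.5% | 17.8% / 8.9% |
| 10 | 40.1% / 22.4% | 28.7% / 14.4% | 21.3% / 10.7% |

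For example, 1 − 0.95^10 = 0.401 and 1 − 0.975^10 = 0.224. Across k = 7 to 10 the range is 17.8–40.1% in either direction and 8.9–22.4% for the higher dose.

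A less uniform pattern stays inside that range. With correlation 0.7 between visits of the same outcome and 0.3 between outcomes, simulation gives 30.4% / 15.4% for k = 10 and 25.0% / 12.6% for k = 7.

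**Why week 48 may not count.** The protocol states: "And 8 months after the first injection, all the patients underwent second injection of the higher-dose method". Eight months is 8 × 30.4375 / 7 = 34.8 weeks, and 48 − 34.8 = 13.2. Week 48 of the first period therefore falls about 13 weeks after the second injection and cannot be a measurement of the average dose alone.

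**The case against.** Three objections have force.

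First, a reader might take 21–40%, the range for 10 tests, as the chance of a false claim for the higher dose. It is not. It counts false differences in both directions; those favouring the higher dose are about half, 10.7–22.4%.

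Second, a reader might infer that every outcome is tested at every visit. The protocol says when data were collected, not what is tested when, so any value of k is an assumption. On the narrowest view only intensity and duration bear on the title's question. Exposure at weeks 4 and 12 plus a duration comparison gives k = 3, and favouring the higher dose that is 1 − 0.975^3 = 7.3% if independent and 5.5% at ρ = 0.7. These figures are much smaller, but still more than twice the 2.5% for a single test. The uncertainty over k changes the size of the problem and does not remove it.

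Third, a reader might take the closing sentence of the plan as a rule that any one P<0.05 establishes superiority. It sets a threshold for each test and says no more. The defect is an omission: nothing identifies which comparison carries the conclusion, and nothing controls error if several may do so.

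It can also be said that this is a small study for which a short plan is normal. That does not help a reader decide which of several P values answers the title's question.

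**Conclusion.** The concern holds as a gap in error control. With four unranked aims, three visits, one per-test threshold and no primary comparison, the error rate for the set of tests exceeds that of a single test at every count examined. Under 7 to 10 unadjusted two-sided tests, common correlation 0 to 0.7 and a global null, it is about 18–40% in either direction against 5%, and about 9–22% favouring the higher dose against 2.5%. Even 4 tests give about 13–19% and 6.5–10%. The test count, sidedness and correlation are assumptions, so these figures should be quoted only as ranges.

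The calculation covers chance error alone. Every participant receives the average dose first and the higher dose second; bias from that fixed order is a separate matter which no multiplicity rule corrects.

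**What to change.** Before the data are examined, replace the single-threshold sentence with a fixed sequence, each step at two-sided 0.05:

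1. Anterior gingival exposure at week 4, higher versus average dose, as the measure of intensity.
2. Only if step 1 is significant, anterior gingival exposure at week 12, higher versus average dose, declared as the operational measure of duration. The documents do not define duration, so this is a choice that the plan must state.

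Report all other comparisons as descriptive, or test them by Holm only if both primary tests are significant. The gate matters: a Holm family at 5% run alongside the primary sequence regardless of its result would give about 1 − 0.95^2 = 9.75% overall if the two were independent.

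Do not make week 48 primary. The follow-up schedule and the timing of the second injection must be reconciled in the protocol.

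Much of the plan is written in the past tense, so it is unclear whether outcomes had already been seen. If they had, a primary comparison chosen now gives no protection, and the results should be reported as exploratory.

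The cost is modest. Some secondary results with P below 0.05 can no longer be called significant: with 8 secondary tests, the smallest P must fall below 0.05/8 = 0.00625 under Holm. Duration cannot be claimed if the week-4 test fails. No extra data collection is needed.
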